4.2.4 Handling of missing data for prior and concomitant medications

Any medications with incomplete start and end dates/times will be handled according to the following rules for classification as prior and concomitant and for the calculation of relative study days. In the event of ambiguity or incomplete data which makes it impossible to determine whether a medication was concomitant or not, the medication will be considered as concomitant. Such imputations will only be performed for these classifications and calculations; in the listings all data will be shown as recorded on the eCRF.

Imputation of partial start dates

- If only the month and year are specified:
 - if the month and year of first dose of IMP is not the same as the month and year of the start date and the subject did not switch from placebo to BKZ at Week 16 during that month and year, then use the 1st of the month.

- if the month and year of first dose of IMP is the same as the month and year of the start, then use the date of first dose of IMP.
 - if the subject did switch from placebo to BKZ at Week 16 during that month and year, then use the date of treatment switch.
- If only the year is specified:
 - If the year of first dose of IMP is not the same as the year of the start date and the subject did not switch from placebo to BKZ at Week 16 during that year, then use the 1st of January of the year of the start date.
 - If the year of first dose of IMP is the same as the year of the start date, then use the date of first dose of IMP.
 - if the year of first dose of IMP is the same as the year the subject did switch treatment from placebo to BKZ at Week 16, then use the date of treatment switch.
 - if the year of first dose of IMP is the same as the year of the start date and the same as the year the subject did switch from placebo to BKZ at Week 16, then use the date of first dose of IMP.
- If the start date is completely unknown:
 - if the stop date is unknown or not prior to the date of first dose of IMP, then use the date of first dose of IMP.
 - if the stop date is prior to the date of first dose of IMP, then set the start date to the 1st of January of the year of the end date.

Imputation of Partial Stop Dates:

- If only the month and year are specified, then use the last day of the month,
- If only the year is specified, then use December 31st of that year.
- If the stop date is completely unknown, do not impute the stop date. There will be no imputation of any other missing data.

If the imputed stop date is prior to the imputed start date:

- For missing start day and start month:
 - If the year of start date is the same as the year of first dose and the imputed stop date is on or after the date of first dose, then set the start date to the date of first dose
 - Otherwise set to the 1st January of the year of the start date.
- For missing start day only
 - If the month and year of the start date is the same as the month and year of first dose and the imputed stop date is on or after the date of first dose, then set the start date to the date of first dose

- If the month and year of the start date is the same as the month and year of first dose and the imputed stop date is before the date of first dose, then set the start date to the 1st of that month.

In the event of ambiguity or incomplete data which makes it impossible to determine whether a medication was concomitant, the medication will be considered as concomitant.

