2.3.2.3 Active Treatment-Blind Period

After the 16-week DBP, subjects will enter the 36-week ATP. At Week 16 (Visit 10), subjects will be allocated to treatment regimens as follows:

- Subjects in the BKZ 160mg sc Q4W group will continue to receive BKZ 160mg sc Q4W
- Subjects in the placebo group will be reallocated to BKZ 160mg sc Q4W Subjects in the ADA 40mg sc Q2W group will continue to receive ADA 40mg sc Q2W.

As for the DBP, BKZ and ADA will be administered sc by unblinded study personnel at the clinical site. The first dose in the ATP will be administered at Week 16 after all assessments have been completed.

During the 36 weeks of the ATP, IMP administration will be performed every 2 weeks (allowed visit window between 11 and 17 days) at Study visits (from Visit 10 – Week 16 through Visit 27 - Week 50).

Visit 28 (Week 52) ends the ATP, and the last assessments for that period are collected during that visit.

Subjects who withdraw early from the study will undergo the ET visit assessments and will enter the SFU Period, as applicable. Subjects who withdraw from IMP during the ATP will be encouraged to return for all remaining scheduled visits up to Week 52 and the SFU visit (20 weeks after their final dose of IMP).

At the completion of the ATP, investigators should discuss treatment options with the subject. Subjects who complete PA0010 (ie who performed all visits up to Week 52 and not having permanently discontinued IMP and who did not meet any of the withdrawal criteria) will be given the opportunity to enter the OLE study at Week 52.

The ATP starts on the day of dose administration at Week 16 and ends at Week 52 (Visit 28) or at the Early Termination visit (ET Visit) for subjects withdrawn from the study after Week 16 and before Week 52. This period should last 36 weeks maximum.

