4.2.3 Handling of missing data for AEs

For analyses of AEs, a complete date must be established to correctly identify the AE as occurring during treatment or not. For purposes of imputing missing components of partially reported start and stop dates for AEs, the algorithms listed below will be followed. In the event of ambiguity or incomplete data which makes it impossible to determine whether the AE was treatment-emergent, the AE will be considered treatment-emergent.

Although the algorithms for treatment-emergence depend on the start date, imputation rules are provided for stop date as well, as these may be needed for certain statistical analyses, such as an analyses of AE prevalence or AE duration.

Start and stop dates of AEs will be displayed as reported in the subject data listings (ie, no imputed values will be displayed in data listings).

Imputation of partial AE start dates

- If only the month and year are specified:
 - if the month and year of first dose of IMP is not the same as the month and year of the start date, then use the 1st of the month
 - if the month and year of first dose of IMP is the same as the month and year of the start date, then use the date of first dose of IMP
 - if the subject did switch treatment during that month and year from placebo to BKZ at Week 16, then use the date of treatment switch.
- If only the year is specified:
 - if the year of first dose is not the same as the year of the start date, and if the subjects did not switch from placebo to BKZ at Week 16 during that year then use January 1 of the year of the start date
 - if the year of first dose is not the same as the year of the start date, and if the subjects did switch from placebo to BKZ at Week 16 during that year then use the date of treatment switch
 - if the year of first dose is the same as the year of the start date and the same as the year the subject did switch from placebo to BKZ at Week 16, then use the date of first dose.
- If the date is completely unknown:
 - use the date of first dose of IMP if the stop date is unknown or not prior to the onset date

Imputation of Partial Stop Dates

- If only the month and year are specified, then use the last day of the month
- If only the year is specified, then use December 31st of that year
- If the stop date is completely unknown, do not impute the stop date.

If the imputed stop date is prior to the imputed start date:

- For missing start day and start month:

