6.4 Prior and concomitant medications

Prior medications include any medications that started prior to the date of the first IMP administration.

Concomitant medications are medications taken at least one day in common with the IMP dosing period.

The IMP dosing period corresponding to the combined DBP and ATP will be calculated as follows:

The study medication dosing period start date is defined as the date of first dose.

The study medication dosing period stop date is defined as follows:

- For subjects who are ongoing at the time of the clinical data cut (not including participants who are in SFU) use date of last clinical contact
- For subjects who died prior to last visit (not including those who died during SFU), use the minimum of the following:
 - Date of death
 - Date of last dose of any study medication + 28 days
- For subjects who complete the study as planned, the dosing period ends at the later of the following 2 dates:
 - Date of last administration of IMP + 14 days
 - The last scheduled visit date not including SFU
- For all other subjects, use the maximum of the following:
 - Date of last dose of any study medication + 28 days
 - Date of last visit (not including SFU).

In the case of missing data, the classification of medications as prior or concomitant will be performed as described in [Section 4.2.4](#). Imputations of missing data will be performed before calculation of relative study days.

The number and percentage of subjects taking prior medications (excluding past psoriasis medications) will be summarized on the SS by treatment group, overall and by ATC class, presenting Anatomical Main Group (ATC Level 1), Pharmacological Subgroup (ATC level 3) and PT.

The table summary will be ordered alphabetically for the ATC class and in terms of decreasing frequency for PT within ATC class in the BKZ treatment group. In the event of ties, PT will be ordered alphabetically.

The number and percentage of subjects taking concomitant medications will be summarized similarly on the SS by treatment group (for the Week 24 analysis on the period from Baseline to Week 24, for the Week 52 analysis on the overall study treatment period).

A by-subject listing of all prior (on the RS) and concomitant medications (on the RS) as well as glossary of all medical medications will be provided.

6.5 Prohibited medications and permitted rescue therapy after Week 16

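### In SAP Section 4.2.4 the third year-only start-date rule leaves out the medication's own start year, so some placebo-arm records get two conflicting dates and others get none

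*SAP*

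**What the plan says.** SAP Section 4.2.4 gives four rules for a start date of which only the year is known. They are numbered here in printed order; the SAP does not number them.

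- **Rule 1:** "If the year of first dose of IMP is not the same as the year of the start date" and there was no switch in that year, "then use the 1st of January of the year of the start date".
- **Rule 2:** "If the year of first dose of IMP is the same as the year of the start date, then use the date of first dose".
- **Rule 3:** the switch date is used whenever "the year of first dose of IMP is the same as the year the subject did switch treatment from placebo to BKZ".
- **Rule 4:** if dose year, start year and switch year all coincide, use the first-dose date.

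The matching adverse-event rule in Section 4.2.3 applies when the first-dose year differs from the start year: "if the subjects did switch from placebo to BKZ at Week 16 during that year then use the date of treatment switch". There, the year meant is the start year of the event.

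Only one arm switches (Section 2.3.2.3): "Subjects in the placebo group will be reallocated to BKZ 160mg sc Q4W". Section 6.4 defines the flag that depends on the imputed date: "Prior medications include any medications that started prior to the date of the first IMP administration".

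**The concern.** Rule 3 imputes a medication's start date without using the only part of that date that was recorded. The neighbouring rules do use it. The month-and-year rule in the same section requires the switch to fall in the recorded month and year, and the adverse-event rule requires it to fall in the recorded year. Rule 3 reads like a miswording of the adverse-event rule.

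At stake is whether the same record is dated the same way by any two programmers, and in every arm. A drug taken for years before the trial should count as prior medication. If rule 3 prevails it appears to start at Week 16 and drops out of the prior-medication table. This can happen only in the placebo arm, so the table by treatment group would be distorted differentially.

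**Working it through.** The plan gives no figure to reproduce. The check applies the four rules literally, with the switch at first dose + 112 days (16 weeks; Section 10.1.1.2 gives 112 days for the period).

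**Example A:** first dose 2020-03-02, switch 2020-06-22 (same calendar year).
**Example B:** first dose 2019-11-04, switch 2020-02-24 (next calendar year).

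| Case | Start year | Placebo subject | Non-switching arm | Placebo, rule 3 reworded |
|---|---|---|---|---|
| A | 2012 | rule 1: 2012-01-01; rule 3: 2020-06-22 | 2012-01-01 | 2012-01-01 |
| A | 2020 | rules 2 and 4: 2020-03-02; rule 3: 2020-06-22 | 2020-03-02 | 2020-03-02 |
| B | 2012 | rule 1: 2012-01-01 | 2012-01-01 | 2012-01-01 |
| B | 2020 | no rule applies | 2020-01-01 | 2020-02-24 |

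**Does an implied order settle it?** Section 4.2.4 states none.

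- *First match wins.* After rules 1 and 2, the only case left is a start year that differs from the dose year, with the switch in the start year. The switch year then differs from the dose year, so rules 3 and 4 can never apply. Older drugs are dated correctly, but the last row of the table still has no date.
- *Last match wins.* Rule 4 restores the first-dose date for drugs from the dose year. Rule 3 overrides rule 1, and the 2012 drug is dated 2020-06-22. The last row still has no date.

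Rules 3 and 4 therefore have an effect only on the reading that misdates older drugs, and the gap remains on both readings.

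**Does the stop-before-start correction help?** It needs an imputed stop date that precedes the imputed start. Section 4.2.4 does not impute a wholly unknown stop date, so an ongoing drug never triggers it.

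**Which classifications can change?** Only the first row changes prior status: 2012-01-01 precedes first dose and 2020-06-22 does not. In the second row neither date precedes first dose, so the drug is not prior either way. An ongoing drug overlaps the dosing period under either date, because a subject who switched was dosed at the switch. It stays concomitant.

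**How many subjects are exposed?** Rule 3 applies only when first dose and switch share a calendar year. In a 365-day year that holds for the first 365 − 112 = 253 days. With first doses spread evenly, 253/365 = 69.3%, and 280 × 253/365 ≈ 194 of the planned 280 placebo subjects, if all switch. The document gives no enrolment dates. The share could lie anywhere from 0% (all first doses in the last 112 days of a year) to 100% (none in them).

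**The case against.** The strongest answer is that rule 1 also covers the older drug and gives the right date. A reader might infer from rule 3 that long-standing drugs *are* dated to the switch. The text does not establish that: it leaves two rules in conflict, and misdating follows only if rule 3 prevails. This stands and limits the claim. It does not clear the text, because the first-match reading makes rules 3 and 4 inoperative and leaves the gap.

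A reader might also infer that rescue reporting is contaminated, since permitted rescue begins after Week 16. The document does not support this. Section 4.2.4 confines these imputations to the prior/concomitant classification and relative study days, and listings show dates as recorded. Section 6.5 refers to the protocol for permitted rescue and does not say that rescue is identified from imputed start dates.

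The consequences are also small. The prior-medication table is descriptive and already excludes past psoriasis medications (Section 6.4). Prior cDMARDs for the subgroups are classified from an adjudicated spreadsheet (Section 4.8). Even the effect on relative day is uncertain: Section 3.2.1 leaves it missing for partial dates, while Sections 4.2.4 and 6.4 impute before calculating it. All of this stands.

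**Conclusion.** The drafting fault is real and minor. Rule 3 omits the medication's start year. It therefore conflicts with rule 1 for older drugs and with rules 2 and 4 for drugs from the dose year, and the switch-year case has no rule. All three faults occur only in the placebo arm.

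The documented effect is on the prior flag for older ongoing drugs with year-only starts, conditional on rule 3 overriding rule 1, and possibly on relative day. Concomitant status of these drugs and the primary analysis are not affected.

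The 69% rests on evenly spread first doses. It is the share of placebo subjects for whom rule 3 can apply, not a rate of wrong dates. The document does not show how many year-only, ongoing records there are.

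**What to change.** Replace the third year-only bullet of Section 4.2.4 by:

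> If the year of the start date differs from the year of first dose of IMP and the subject switched from placebo to BKZ at Week 16 during the year of the start date, use the date of treatment switch.

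Keep the first two bullets. The fourth is then redundant but harmless. This follows the logic of the adverse-event rule in Section 4.2.3, and every case in the table gets exactly one date, including the one that now has none. Stating an order of precedence alone would not be enough, because no order fills that gap. The cost is one bullet of SAP wording and the matching line of the date-imputation program.

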4.3 Planned analyses and data monitoring

4.3.1 Interim analyses & final analysis

Two interim analyses will be performed:

- Interim analysis 1: Week 24 analysis.

The Week 24 analysis is the first interim analysis after all randomized subjects have completed the DBP and the ATP up to Week 24 or have withdrawn from the IMP or the study before Week 24. The purpose of this analysis is to perform a comprehensive evaluation of all available data for the 3 treatment arms to prepare a regulatory submission for a marketing authorization application based on this analysis. This interim analysis will cover the analysis of all efficacy and non-safety by visit tables on data collected up to Week 24 and the analysis of safety in tables on data collected up to the cut-off date (defined as Week 24 visit) for the last subject (all available data will be reported in listings). The type of efficacy and safety tables provided for the first interim analysis is detailed in [Table 4-4](#).

For this analysis, the database will be cleaned and locked, and the treatment codes will be made available to the independent unblinded UCB and PAREXEL personnel. The database will include all data available at the time of the lock including available SFU data (for subjects having completed the SFU Period). An interim report will be written. The investigators and the subjects will remain blinded until the final analysis is completed. A blinding plan will be written to ensure blinding of investigators and subjects, define blinded and unblinded teams at UCB and PAREXEL and describe the process of generation and dissemination of the results of this first interim analysis. This plan will be finalized prior to the lock of the database for this analysis.

- Interim analysis 2: Week 52 analysis.

The Week 52 analysis is the second interim analysis after all subjects have completed Week 52 or have withdrawn from the IMP or the study. The purpose of this analysis is to demonstrate the long-term efficacy and safety of BKZ, perform a comprehensive evaluation of all available data for the study and to supplement the regulatory submission based on the Week 24 interim analysis. This analysis will comprise the results of the 16 weeks of the DBP, the 36-weeks of the ATP and the available SFU data at the time of this analysis (for subjects having completed the SFU Period). The type of efficacy and safety tables provided for the second interim analysis is detailed in [Table 4-4](#).

No formal alterations to the further study conduct (eg, stopping rules, sample size re-estimation, or changes to eligibility criteria) are planned for the 2 interim analyses.

No separate SAP for the interim analyses will be provided. The TFL shells for the interim and the final analyses will be provided in the same document and appropriately identified.

The below table summarize the type of efficacy and safety analyses to be performed for the 2 interim analyses.

Table 4-4: Type of efficacy and safety tables provided for the interim analyses

Variable Type of tables	Period or Timepoint (Analysis set)	Treatment groups	Provided for Interim Analysis 1 (Week 24 analysis)	Provided for Interim Analysis 2 (Week 52 analysis)
Tables of primary efficacy variable	Week 16 (RS FAS PPS)	
 • Placebo • BKZ 160mg Q4W • ADA 40mg Q2W 	Yes	Yes, rerun of tables provided for interim analysis 1
Tables of secondary efficacy variables.	Week 4 and 16 (RS*)	
 • Placebo • BKZ 160mg Q4W • ADA 40mg Q2W 	Yes	Yes, rerun of tables provided for interim analysis 1
Tables / Graphs of time to ACR response	DBP (RS)	
 • Placebo • BKZ 160mg Q4W • ADA 40mg Q2W 	Yes, subjects not achieving response at Week 16 are censored at Week 16.	Yes, rerun of tables provided for interim analysis 1
	Overall Study Period (RS)	
 • Placebo/BKZ 160 mg Q4W • BKZ 160mg Q4W • ADA 40mg Q2W 	Yes, subjects not achieving response at Week 24 are censored at Week 24.	Yes, subjects not achieving response at Week 52 are censored at Week 52.
By-visit tables of other efficacy endpoints	Overall Study Period (RS*)	
 • Placebo / BKZ 160 mg Q4W • BKZ 160mg Q4W • ADA 40mg Q2W 	Yes, from Baseline to Week 24	Yes, from Week 0 until Week 52.
Extra by-visit tables for ACR50 and PASI90 using Baseline Week 16	ATP (ATS)	
 • Placebo / BKZ 160mg Q4W 	Yes, from Week 20 until Week 24	Yes, from Week 16 until Week 52.
Extent of exposure and time at risk	DBP (SS)	
 • Placebo • BKZ 160mg Q4W • ADA 40mg Q2W 	Yes	Yes
	ATP (ATS)	
 • Placebo / BKZ 160mg Q4W • BKZ 160mg Q4W • BKZ 160mg Q4W Total • ADA 40mg Q2W 	Yes, until Week 24	Yes
	AMP (AMS)	
 • Placebo / BKZ 160mg Q4W • BKZ 160mg Q4W • BKZ 160mg Q4W Total • ADA 40mg Q2W 	Yes, until Week 24	Yes
Cumulative study medication duration	Overall Study Period (SS)	
 • Placebo / BKZ 160mg Q4W • BKZ 160mg Q4W • ADA 40mg Q2W 	Yes, until Week 24	Yes

Variable Type of tables	Period or Timepoint (Analysis set)	Treatment groups	Provided for Interim Analysis 1 (Week 24 analysis)	Provided for Interim Analysis 2 (Week 52 analysis)
Tables of AEs or Tables of AEs of Special Interest or Tables of Other Safety Topics of Interest.	DBP (SS)	
 Placebo BKZ 160mg Q4W ADA 40mg Q2W 	Yes	Yes
	ATP (ATS)	
 Placebo / BKZ 160 mg Q4W BKZ 160 mg Q4W BKZ 160mg Q4W Total ADA 40mg Q2W 	Yes, until cut-off date for this analysis	Yes
	AMP (AMS)	
 BKZ 160mg Q4W Total ADA 40mg Q2W 	Yes, until cut-off date for this analysis	Yes, for treatment-emergent events until Week 52 and including available SFU data
By-visit and shift tables of laboratory data or vital signs	Overall Study Period (SS)	
 Placebo / BKZ 160mg Q4W BKZ 160mg Q4W ADA 40mg Q2W 	Yes, until cut-off date for this analysis	Yes, for all visits until Week 52
Tables of markedly abnormal laboratory values or vital signs	DBP (SS)	
 Placebo BKZ 160mg Q4W ADA 40mg Q2W 	Yes	Yes
	ATP (ATS)	
 Placebo / BKZ 160mg Q4W BKZ 160mg Q4W BKZ 160mg Q4W Total ADA 40mg Q2W 	Yes, until cut-off date for this analysis	Yes
	AMP (AMS)	
 BKZ 160mg Q4W Total ADA 40mg Q2W 	Yes	Yes
By-visit tables of ECG, table of ECG abnormalities	Overall study period (SS)	
 Placebo / BKZ 160mg Q4W BKZ 160mg Q4W ADA 40mg Q2W 	Yes, until cut-off date for this analysis.	Yes, for all visits until Week 52.
Table of eC-SSRS events.	Overall Study Period (SS)	
 Placebo / BKZ 160mg Q4W BKZ 160mg Q4W ADA 40mg Q2W 	Yes, until cut-off date for this analysis	Yes
Table of tuberculosis testing.	Screening and W48 (SS)	
 Placebo / BKZ 160mg Q4W BKZ 160mg Q4W ADA 40mg Q2W 	Yes, Screening and Week 48 values (if observed prior to cut-off date).	Yes, Screening and Week 48 value.

ACR= American College of Rheumatology, ADA=Adalimumab, AE=adverse events, ATP=Active Treatment-Blind Period, ATS=Active Treatment-Blind Set, AMP=Active Medication Periods, AMS=Active Medication Set, BKZ=Bimekizumab, DBP=Double-Blind Treatment Period, eC-SSRS=electronic Columbia Suicide Severity Rating Scale, ECG=electrocardiogram, FAS=Full Analysis Set, PASI= Psoriasis Area and Severity Index, RS=Randomized Set, SS=Safety Set

*For subjects in the Radiographic Set for vdHmTSS

Note: Subjects in the Placebo/ BKZ 160mg Q4W treatment group are taking BKZ 160 mg Q4W treatment after Week 16.

- The final analysis.

The final analysis will consist of a rerun of all analyses provided during the preceding Week 52 analysis. This includes new SFU data that were not available for the Week 52 analysis. If there is no SFU data ongoing, the final analysis will be identical to the Week 52 analysis.

Prior to the final analysis, additional data cuts may be prepared following regulatory requests or for publication purposes.

